# Please rate the extent to which you had each symptom during the past 24 hours.

## In the past 24 hours, how often have you had any of the following symptoms?

	Never	Rarely	Sometimes	Often	Always
Sneezing					
Coughing					
Coughed up mucus or phlegm					

	0 times	1 time	2 times	3 times	4 or more times
How many times did you vomit?					
How many times did you have diarrhea?					

Participant Initials:	Date:	/	/	
	Participant Initials:	Participant Initials:Date:	Participant Initials:Date:/	Participant Initials:Date:/ /

Items to be asked in the daily diary through to Day 15 along with the Flu-PRO items.

- 1. Overall, how severe were your flu symptoms today? (Please select one response only)
- $\Box$  0 No flu symptoms today
- 1 Mild
- 2 Moderate
- 3 Severe
- 4 Very severe

2. [Skip this question if you answered 0 above]. Overall, how were your flu symptoms today compared to yesterday? (Please select one response only)

- 1 Much better
- 2 Somewhat better
- 3 A little better
- 4 About the same
- 5 A little worse
- 6 Somewhat worse
- 7 Much worse

3. [Skip this question if you answered 0 in Question #1]. How much did your flu symptoms interfere with your activities today? (Please select one response only)

- 1 Not at all
- 2 A little bit
- 3 Somewhat
- 4 Quite a bit
- 5 Very much
- 4. Have you returned to activities today?
- 0 No
- 1 Yes

5. In general, how would you rate your physical health today? (Please select one response only)

- 1 Poor
- 2 Fair
- 3 Good
  - 4 Very Good
- 5 Excellent
- 6. Are you in your usual state of health today?
- 0 No
- 1 Yes

1. PREFACE

The Statistical Analysis Plan (SAP) for DMID Protocol 20-0005, A Multicenter, Blinded, Randomized, Placebo Controlled, Dose-Ranging Influenza Challenge Study in Healthy Adult Volunteers to Determine the Optimal Infection Dose and Safety of a Recombinant H3N2 (A/Texas/71/2017 (H3N2), clade 3C3a) Influenza Challenge Virus, describes and expands upon the statistical information presented in the protocol.

This document describes all planned analyses and provides reasons and justifications for these analyses. It also includes sample tables, listings, and figures planned for the final analyses. Regarding the final analyses and Clinical Study Report (CSR), this SAP follows the International Conference on Harmonisation of Technical Requirements for Registration of Pharmaceuticals for Human Use (ICH) Guidelines, as indicated in Topic E3 (Structure and Content of Clinical Study Reports), and more generally is consistent with Topic E8 (General Considerations for Clinical Trials) and Topic E9 (Statistical Principles for Clinical Trials).

This document contains four overarching sections: (1) a review of the study design, (2) general statistical considerations, (3) comprehensive statistical analysis methods for safety, efficacy, and immunological or other biomarker outcomes, and (4) a list of proposed tables and figures. Any deviation from this SAP will be described and justified in future amendments and/or in the CSR, as appropriate. The reader of this SAP is encouraged to also review the study protocol for details on conduct of the study and the operational aspects of clinical assessments.

2. INTRODUCTION

Despite current vaccination strategies and the availability of antivirals, influenza remains a leading cause of mortality, hospitalizations, missed work, missed school and economic disruption across the globe. Improved prevention and management approaches for seasonal and pandemic influenza across all populations are urgently needed, including the development of new universal vaccines that offer broad and robust protection. The human challenge model is a powerful tool for efficiently and safely determining the effectiveness of prevention and treatment options for influenza in a shorter timeframe and with a smaller number of participants compared to typical clinical trials, using a well-characterized virus strain. DMID Protocol 20-0005: A/Texas/71/2017 (H3N2) Dose-ranging Challenge Study is designed to determine the optimal infectious dose of the H3N2 (A/Texas/71/2017 (H3N2), clade 3C3a) influenza virus challenge strain for use in future Phase I clinical trials evaluating vaccine candidates. The study was designed to enroll and challenge up to 106 healthy adult volunteers with the H3N2 (A/Texas/71/2017 (H3N2), clade 3C3a) influenza virus challenge strain, plus approximately 8 participants receiving sham inoculum (saline) to allow for blinding. Participants were pre-screened for study inclusion to ensure enrolled participants have serological HAI antibody titers of $\leq 1:40$ against the clinical challenge strain. Eligible participants were to be enrolled sequentially into dosing cohorts and randomly assigned to receive a single dose of either sham inoculum or a virus dose between 10^4 to 10^6 TCID₅₀ (in an allocation of 1:12 for the two lower dose levels and 1:17 at the highest dose level). Dose titration was to be conducted under an adaptive escalation schedule (see [Figure 1](#)), with dosing starting at the lowest dose (10^4 TCID₅₀) and only escalating to the next dose if a pre-determined infection and symptomatic attack rate was not met and the dose was determined to be safe with no pre-defined halting rule met. The attack rate (AR), defined as the percentage of participants meeting shedding and symptom criteria for symptomatic influenza virus infection (see clinical case definition in [Section 3](#)), will be determined for each challenge dose group in order to identify the optimal infectious dose (with a targeted 55%-80% AR). This adaptive, dose-ranging approach allows adjustments to challenge dose group size and escalation dose schedule to be informed by the AR and safety results.

2.1. Purpose of the Analyses

This study was designed to find a safe but infectious dose of the H3N2 (A/Texas/71/2017 (H3N2), clade 3C3a) influenza virus challenge strain to utilize in future vaccine studies. In addition to determining the rate of symptomatic influenza infection in each challenge dose group, the goals of the study include further characterization of the viral shedding and symptoms post-infection, describing the safety profile of the challenge virus, and to assess the immune response to infection.

This analysis plan covers the primary and secondary objectives of the study, along with exploratory objectives relating to available clinical data, which will be reported in the Clinical Study Report (CSR). The remaining exploratory objectives utilizing additional immunological, genomic, and/or transcriptomic data that will not be available at the time of the compilation of the primary CSR will be addressed in addenda to this analysis plan and presented in CSR addenda or separate standalone reports for the development of manuscripts.

3. STUDY OBJECTIVES AND ENDPOINTS

3.1. Study Objectives and Endpoints

The study objectives and endpoints addressed in this SAP are presented below. The remaining exploratory objectives not included this SAP will be addressed in addenda to this analysis plan.

OBJECTIVES	ENDPOINTS (OUTCOME MEASURES)
Primary	
1. To determine the optimal infectious dose ¹ of a recombinant influenza virus (A/Texas/71/2017 (H3N2), clade 3C3a) to be used as a clinical challenge strain in future vaccine efficacy or intervention studies as assessed by viral shedding and clinical symptoms	a. Percentage of participants within a challenge dose group with detectable shedding in nasopharyngeal (NP) swab(s) by RT-PCR over any 2 days beginning 24 hours post challenge through Day 8 and with symptom scores that meet the clinical case definition for symptomatic infection (Modified Jackson score). See Section 3.2 for the clinical case definition for symptomatic infection.
2. To describe viral detection by quantitative and qualitative RT-PCR from study participants at baseline and post-challenge	a. Percentage of participants within a challenge dose group with detected viral shedding in NP swab(s) each day post-challenge from Day 2 through Day 8 using qualitative RT-PCR and quantitative RT-PCR b. Magnitude of virus shedding post-challenge in each participant defined as the peak viral load in NP swab(s) from day 2 through Day 8 post-challenge by quantitative RT-PCR c. Duration of viral shedding defined as the number of days from first positive RT-PCR to last positive RT-PCR where virus is detected in NP swab(s) by quantitative or qualitative RT-PCR post challenge day 1 for each participant
3. To document clinical symptoms from self-reported surveys and standardized symptom scales at baseline and post challenge	a. Computed total symptom score from modified Jackson score through Day 8 and at Day 15. b. Percentage of participants with total symptom scores that define symptomatic or asymptomatic categories based on modified Jackson score for each participant

OBJECTIVES	ENDPOINTS (OUTCOME MEASURES)
Secondary	
1. To assess the safety profile of a live recombinant influenza strain (A/Texas/71/2017 (H3N2), clade 3C3a) following challenge in healthy adult volunteers	
 a. Number of adverse events (AE) reported from challenge through Day 29 b. Percentage of participants reporting any AE from challenge through Day 29 c. Number of serious adverse events (SAE) from challenge through Day 57 d. Percentage of participants reporting an SAE at any time from challenge through Day 57
2. To describe the host serum antibody responses at baseline and post-challenge	
 a. Percentage of participants with serological conversion defined as a minimum 4-fold rise in post-challenge serum antibodies (HAI and MN) to influenza infection at Days 8, 15, and 29, or latest time point available, post challenge compared to baseline (Day -1). b. HAI and MN antibody geometric mean titers (GMTs) at baseline (Day -1) and GMTs and Geometric Mean Fold Rise (GMFR) post-challenge at Days 8, 15, and 29, or latest time point available
3. To describe anti-HA-stalk antibody titer at baseline and post-challenge	
 a. Percentage of participants with serological conversion defined as a minimum 4-fold rise in post-challenge HA-stalk specific serum antibody response to HA group 2 stem domains at any day up to Day 29, or latest time point available, post challenge compared to baseline (Day -1). b. For HA-stalk specific response, the GMTs to HA group 2 stem domains at baseline (Day -1), and GMTs and GMFR at approximately Days 8, 15, and 29, or latest time point available.
Exploratory	
1. To describe the host serum neuraminidase inhibiting antibody responses at baseline and post-challenge	
 a. Percentage of subjects with serological conversion defined as a minimum 4-fold rise in post-challenge serum antibodies (NAI) to influenza infection at Days 8, 15, and 29, or latest time point available, post challenge compared to baseline (Day -1).

OBJECTIVES	ENDPOINTS (OUTCOME MEASURES)
	b. NAI antibody geometric mean titers (GMTs) at baseline (Day -1) and GMTs and Geometric Mean Fold Rise (GMFR) post-challenge at Days 8, 15, and 29, or latest time point available
5. To compare the clinical features of symptomatic RT-PCR-positive and RT-PCR-negative illness post-challenge	a. Self- and investigator-solicited report of clinical symptoms and their severity as measured by component questions in FLU-PRO and Validation Diary and modified Jackson score by post-challenge Study Day 15 and qualitative RT-PCR positive status
6. To explore alternative case definitions (e.g., MMID or MMID-2) for symptomatic RT-PCR-positive influenza virus infection	a. The combination of symptoms and symptom severity as determined by report using the FLU-PRO and Validation Diary or modified Jackson score which optimize sensitivity and/or specificity for classifying influenza virus infection based on qualitative RT-PCR.
7. To determine the symptomatic background within uninfected participants and between sites	a. Compare symptoms from participants inoculated with shams to participants inoculated with virus

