1. To assess the safety profile of a live recombinant influenza strain (A/Texas/71/2017 (H3N2), clade 3C3a) following challenge in healthy adult volunteers	
 
a. Number of adverse events (AE) reported from challenge through Day 29
 
b. Percentage of subjects reporting any AE from challenge through Day 29
 
c. Number of serious adverse events (SAE) from challenge through Day 57
 
d. Percentage of subjects reporting an SAE at any time from challenge through Day 57
 

2 T. 1	Demonstration of and instances (1 1 1 1
2. To describe the host serum hemagglutination inhibition and microneutralization antibody responses at baseline and post-challenge	
 
a. Percentage of subjects with serological conversion defined as a minimum 4-fold rise in post-challenge serum antibodies (HAI and MN) to influenza infection at Days 8, 15, and 29, or latest time point available, post challenge compared to baseline (Day - 1).
 
b. HAI and MN antibody geometric mean titers (GMTs) at baseline (Day -1) and GMTs and Geometric Mean Fold Rise (GMFR) post-challenge at Days 8, 15, and 29, or latest time point available
 

3. To describe anti-HA-stalk antibody titer at baseline and post-challenge	
 
a. Percentage of subjects with serological conversion defined as a minimum 4-fold rise in post-challenge HA-stalk specific serum antibody response to HA group 2 stem domains at any day up to Day 29, or latest time point available, post challenge compared to baseline (Day -1).
 
b. For HA-stalk specific response, the GMTs to HA group 2 stem domains at baseline (Day -1), and GMTs and GMFR at approximately Days 8, 15, and 29, or latest time point available.
 

Exploratory	
1. To describe the host serum neuraminidase inhibiting antibody responses at baseline and post-challenge	
 
a. Percentage of subjects with serological conversion defined as a minimum 4-fold rise in post-challenge serum antibodies (NAI) to influenza infection at Days 8, 15, and 29, or latest time point available, post challenge compared to baseline (Day -1).
 
b. NAI antibody geometric mean titers (GMTs) at baseline (Day -1) and GMTs and Geometric Mean Fold Rise (GMFR) post-challenge at Days 8, 15, and 29, or latest time point available
 

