#### 9.5.3.2 Analysis of Secondary Immunological Endpoints

Secondary immunological objectives include describing the host serum antibody (HAI and MN) responses and anti-HA-stalk antibody responses at baseline and post-challenge.

For these titer data, GMTs and the proportions of subjects achieving seroconversion, defined as a minimum 4-fold rise in titer post-challenge, will be presented by challenge dose group and visit. Geometric mean fold-rise (GMFR) for anti-HA-stalk antibody titers will be included for post-challenge visits as well. Confidence intervals corresponding to these statistics will be computed for each group and visit as well. Hypothesis testing may be performed for select immunological endpoints and time points, which will be pre-specified in the SAP.

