3.2.7. Immunogenicity Variables

Baseline values for immunogenicity (antibody) will be the last pre-challenge results available.

For individual participants, fold-rise in antibody titers will be calculated as (post-challenge titer)/(pre-challenge titer), where the pre-challenge value is the result obtained at baseline.

Seroconversion for HAI, NAI, MN, and anti-HA stalk assays will be defined as a minimum 4-fold rise in antibody titer from baseline. This corresponds to either a pre-challenge titer $<$ LOD and a post-challenge titer $\geq 4 \times \text{LOD}$, or a pre-challenge titer \geq LOD and a minimum four-fold rise in post-challenge titer.

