8. IMMUNOLOGICAL EVALUATION

8.1. Secondary Immunogenicity Analyses

Only secondary immunogenicity analysis of HAI, MN, NAI, and anti-HA stalk assay data will be included in the interim CSR. Exploratory immunogenicity analysis not included in this SAP will be planned in a separate SAP addendum to this analysis plan and presented in an addendum to the CSR or one or more separate reports for the purposes of manuscript development.

Immunogenicity analyses are planned in the ITT population. If 10% or more of the timepoints utilized in the immunogenicity analyses would be excluded by the list given in [Section 5.3.3](#) to define the Per Protocol population, the secondary immunogenicity analyses will be conducted in the PP population as a sensitivity analysis.

HAI, MN, and anti-HA stalk antibody titers against the challenge strain will be analyzed by time point, challenge dose group, and infection status in [Table 49](#), [Table 50](#), and [Table 52](#), respectively. Geometric mean titers (GMTs) will be computed at each time point for each group, as well as geometric mean fold-rise (GMFR) and seroconversion (as defined in [Section 3.2.7](#)) at each post-challenge time point. Associated 95% CIs will be presented as well. GMTs and 95% CIs will be presented graphically in [Figure 16](#) and [Figure 18](#), and the entire distribution of titers reported at each visit will be presented in reverse cumulative distribution (RCD) curves in [Figure 19](#), [Figure 20](#), and [Figure 22](#).

The assays will be analyzed similarly by symptomatic infection status in [Table 53](#), [Table 54](#), and [Table 56](#).

Antibody titers will be listed, by assay, in [Listing 11](#).

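### Anti-HA-stalk seroconversion is defined as a 4-fold rise on any day through Day 29, but every planned table gives it visit by visit, so secondary endpoint 3a is not estimated

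*SAP*

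**What the plan says.** **Endpoint.** The SAP (section 3.1, secondary objective 3, endpoint a) counts participants with a minimum 4-fold rise over Day -1 in the "HA-stalk specific serum antibody response to HA group 2 stem domains at any day up to Day 29", with an added allowance for the latest available time point. The protocol's endpoint table (section 3) uses the same wording: "response to HA group 2 stem domains at any day up to Day 29, or latest time point available".

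**The neighbouring endpoint reads differently.** For HAI and MN, endpoint 2a names visits: "HAI and MN) to influenza infection at Days 8, 15, and 29, or latest time point available". The exploratory NAI endpoint is also visit-specific. Only stalk seroconversion is written as any-day.

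**Derived variable.** SAP 3.2.7: "Seroconversion for HAI, NAI, MN, and anti-HA stalk assays will be defined as a minimum 4-fold rise in antibody titer from baseline". It sets no time window and has no any-visit version.

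**Analysis.** SAP 8.1 says that "anti-HA stalk antibody titers against the challenge strain will be analyzed by time point, challenge dose group, and infection status", with seroconversion "at each post-challenge time point. Associated 95% CIs will be presented as well". Protocol 9.5.3.2 plans the same: seroconversion, "defined as a minimum 4-fold rise in titer post-challenge, will be presented by challenge dose group and visit".

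**Shells.** Table 52 reuses the Table 49 layout and Table 56 the Table 53 layout. Both have rows for Baseline and Days 8, 15, 29 and 57, and neither has an any-visit row. Table 52 divides each dose group into infected and uninfected, with no combined column. In the Table 49 shell, n at each visit is the number with a result at that visit.

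**The concern.** The endpoint and the analysis are different quantities. The endpoint asks whether a participant ever reached a 4-fold rise by Day 29. The tables ask what fraction had reached it at each draw. Three marginal percentages do not determine the cumulative one, because that depends on how far the same people convert at each visit.

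A named secondary endpoint would therefore have no summary estimate in the clinical study report, and a by-visit percentage could be presented in its place. Table 52 is marked for the topline report, which SAP 5.2 places ahead of the clinical study report, so the mismatch would surface early. The Day 57 row sits beside the others with nothing to say whether it counts toward an endpoint that names Day 29.

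**Working it through.** **Figures in the plan.** Neither document states a stalk seroconversion rate, a fold-rise distribution or a design figure for this endpoint, so there is nothing specific to reproduce. The interval method can be checked on the SAP's own example in 4.4.1: exact Clopper-Pearson for 15/30 gives 31.3% to 68.7%, as stated.

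**Step 1: bounds.** Let p8, p15 and p29 be the proportions converted at each visit, with the same participants measured every time. Then

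max(p8, p15, p29) ≤ P(any day) ≤ min(1, p8 + p15 + p29).

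With assumed rates of 10%, 40% and 30%, the range is 40% to 80%. With 10%, 30% and 30%, it is 30% to 70%. The by-visit rows say no more than this.

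**Step 2: illustrative size.** Assume a trivariate normal threshold model with common between-visit correlation ρ:

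P(any day) = 1 − Φ₃(z8, z15, z29; ρ), with z = Φ⁻¹(1 − p) at each visit.

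| Assumed Day 8/15/29 rates | Highest visit | ρ = 0.95 | ρ = 0.8 | ρ = 0.5 | ρ = 0 |
|---|---|---|---|---|---|
| 10/40/30% | 40% | 41% | 45% | 52% | 62% |
| 10/30/30% | 30% | 34% | 39% | 46% | 56% |

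For ρ from 0.5 to 0.95 the gap above the highest visit is about 1 to 16 points.

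A second parametrisation assumes log2 fold rises with SD 1.3, rounded to 2-fold steps. A 4-fold rise then needs a value of at least 1.5, so p = 1 − Φ((1.5 − mean)/1.3).

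| Assumed means, Day 8/15/29 | Highest visit | Any day, ρ = 0.9 | Any day, ρ = 0.8 | Any day, ρ = 0.6 |
|---|---|---|---|---|
| 0.5/1.8/1.8 | 59.1% | 66.1% | 69.2% | 74.2% |
| 0.5/1.2/1.2 | 40.9% | 48.1% | 51.7% | 57.7% |
| 0.5/1.8/1.3 | 59.1% | 61.1% | 63.7% | 68.6% |
| 0.5/1.8/1.0 | 59.1% | 59.9% | 61.8% | 66.1% |

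With equal Day 15 and Day 29 means the gap is about 7 to 17 points. When the Day 29 mean falls to 1.0 it is 0.7 points at ρ = 0.9.

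**Step 3: when the gap is zero.** If everyone who converts is still converted at one common visit and no titer is missing, the two figures agree: 15/30 = 50% both ways.

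**Step 4: missing titers.** Per-visit denominators are participants with a result at that visit. Follow-up may be by phone (Schedule of Activities footnote), which yields no blood sample, and SAP 5.5 plans no imputation. Take 30 participants, 15 of whom convert by Day 15 and stay converted. Use all 30 as the any-day denominator, since each has at least one post-challenge titer.

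- Five non-converters miss Day 29: Day 29 shows 15/25 = 60%, any-day is 15/30 = 50%.
- Five converters miss Day 29: Day 29 shows 10/25 = 40%, any-day is 15/30 = 50%.

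If the any-day denominator were restricted to participants with all three titers, the first case would give 15/25 = 60%. The denominator rule itself changes the answer, and neither document states one.

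**The case against.** **The objective is descriptive.** It is worded as describing stalk titers, the trial is not powered for any objective (SAP 4.4), and no dose decision uses this result. That stands and limits the consequence. It does not supply the missing estimate.

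**The data are not lost.** Listing 11 reports individual titers, so anyone with the report could derive any-day status. That also stands. What cannot be recovered is the endpoint from the summary percentages.

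**The SAP only follows the protocol.** Protocol 9.5.3.2 already plans presentation by visit. This is correct: the conflict begins inside the protocol, between its endpoint table and its analysis section, and the SAP carries both sides forward.

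**Day 57 may not be out of scope.** The endpoint allows the latest time point available, and protocol Appendix C attaches a similar footnote to the Day 57 serology draw, whose assays include anti-HA-stalk. The window is therefore unclear. An extra descriptive Day 57 row is not an error in itself.

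**A tempting stronger reading.** A reader might infer that the nearest reported percentage must be too low, by some 7 to 17 points. The documents do not support this. That range comes from assumed equal Day 15 and Day 29 means and correlations of 0.6 to 0.9. All fold rises share one baseline titer, which favours high correlation and smaller gaps. The direction is assured only with complete titers, and even then the gap may be zero.

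**Conclusion.** The point holds as a mismatch between endpoint and analysis. Secondary endpoint 3a is cumulative to Day 29, and no planned table or figure in either document estimates it. Table 52 also shows no whole-dose-group column.

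With complete titers the endpoint value is at least the highest of the Day 8, 15 and 29 percentages. The shortfall runs from zero (nested conversion) to about 17 points across the scenarios with correlation of at least 0.5, all of which rest on assumed inputs. With visit-specific missing titers, a single-visit percentage can lie above or below the endpoint value, so no fixed direction or size of error should be claimed. The change is worth making because it lets the trial report an endpoint that it names; no trial decision depends on it.

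**What to change.** 1. **SAP 3.2.7.** Define a participant-level variable: stalk seroconversion at any post-challenge sample through Day 29. State the denominator (for example, participants with a baseline and at least one post-challenge titer in the window). State what the latest-time-point clause means, including whether a Day 57 sample can count.
2. **Tables 52 and 56.** Add a row for this variable with n (%) and a Clopper-Pearson 95% interval. Add an all-participants column per dose group to Table 52, and label its any-day entry as the endpoint 3a result. Keep the by-visit rows as supportive.
3. **Text.** Align SAP 8.1 and protocol 9.5.3.2 with the endpoint table.

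Cost: one derived variable, one row in each of two tables, one extra column per dose group in Table 52, and short text edits in both documents. No additional samples or assays are needed.
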